3.4.1.1 Post-Treatment Withdrawal Flares

The difference between Week 12 and Week 16 laboratory values for ALP, ALT, AST, and GGT will be summarized using descriptive statistics.

3.4.2 *Pruritus VAS*

Change in Pruritus VAS will be summarized using descriptive statistics for the result and change from baseline. The proportion of subjects with improvement will be presented for subjects $>0.5\text{cm}$ at baseline. The proportion of subjects with worsening will be presented for subjects $\leq 0.5\text{cm}$ at baseline.

3.4.3 *Clinical Laboratory Evaluations*

Clinical laboratory results, including bile acids, will be summarized by type of laboratory assessment (hematology, serum chemistry, lipids, coagulation, other) and timepoint. Both central and local laboratory results will be used for the safety lab summaries. Summary statistics for actual values and changes from baseline will be tabulated by analysis window. Out of range clinical laboratory values based upon the normal range will be tabulated for each timepoint. These tables will utilize the normal ranges provided for the individual sample.

The proportion of subjects that cross the liver monitoring thresholds will be summarized. A listing of ALT values for subjects that meet the liver monitoring threshold will be presented similarly to the clinical laboratory listing. Baseline values will be summarized using last available measurement prior to administration of study drug.

3.4.4 *Vital Signs*

The observed data at baseline and change from baseline for each measurement day will be summarized with descriptive statistics.

3.4.5 *Electrocardiogram Results*

The overall ECG assessment (abnormal or normal) will be summarized by analysis window. The QT values will be summarized by analysis window as both the QT value and change from baseline.

3.4.6 *Pregnancy*

A listing of positive pregnancy tests results will be produced.

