### 7.2. Discontinuation of Study Intervention

HTD1801 treatment must be discontinued for a subject if any of the following criteria are met.

- Adverse event that may jeopardize subject's safety
- Grade 3 and above adverse events (AEs) for which the causality is considered as related to investigational agent
- Discontinuation due to drug-induced liver injury (refer to Section 10)
- Request by the subject
- Pregnancy

For subjects who discontinue investigational study drug, an Early Termination Visit should be conducted at the time the investigational study drug is discontinued (see Section 7.3). Subjects who terminate from the study prior to Study Visit Week 12 will be requested to return to the clinic 28 days **after the date of last dose** of investigational study drug and complete the equivalent of the Week 16 follow up visit assessments. If necessary, arrangements can be made with the site and the subject to conduct the visit virtually and make use of a local laboratory for the study required Study Visit Week 16 lab tests.

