2.4 Study Day and Visit Windows

Summary tables will report data based upon the protocol scheduled time points (Baseline, Weeks 2, 4, 6, 8, 12, 16). Assessment will be assigned to these time points based upon the study day they are performed on. Study day is defined as

$$\text{Study Day} = \text{date of assessment} - \text{date of first treatment}.$$

The analysis windows used to report endpoints are outlined in Table 2. Assessments are assigned to an analysis window based upon the study day it occurred on as well as the treatment status at the time the assessment was performed. If more than one assessment is available within the range, the assessment closest to the target day is reported for the analysis window. If two observations exist with the same distance to the target day, the first observation is used.

Table 2 Analysis Windows

Visit	Study Day Range	Target Day	Treatment Status
Screening	< Day -1	First	Off Treatment ^a
Baseline Visit	Day 1	Day 1	Off Treatment ^a
Week 2	Day 2 to Day 21	Day 14	On Treatment ^b
Week 4	Day 22 to Day 35	Day 28	On Treatment ^b
Week 6	Day 36 to Day 49	Day 42	On Treatment ^b
Week 8	Day 50 to Day 70	Day 56	On Treatment ^b
Week 12	Day 71 to Day 90	Day 84	On Treatment ^b
Week 16	> Day 90	Day 112	Off Treatment ^c

^a Prior to first treatment.

^b After the start of treatment to 1 day after the last dose.

^c More than 1 day after the last dose.

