2.6 Handling of Missing Data

Summary statistics will generally be reported based upon observed data. Missing data will not be imputed for the efficacy analyses. Percentages will be reported for subjects with data. Missing dates for AEs and concomitant medications will be imputed to allow these items to be summarized as pre-treatment or not. Should a determination of treatment period (on treatment or pre-treatment) be required for AEs or concomitant medication, but the corresponding date is missing or partial, the event/medication will be considered on treatment unless the portions of the date that are available indicate this is not possible.

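### The withdrawal-flare summary compares Week 12 with Week 16 only, so in effect it leaves out subjects whose last dose is before about Day 70

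*SAP*

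**What the plan says.** SAP 2.3.8.3 names withdrawal flares as a safety item, and SAP 3.4.1.1 gives the analysis: "The difference between Week 12 and Week 16 laboratory values for ALP, ALT, AST, and GGT will be summarized using descriptive statistics". Neither section offers an alternative for a subject who lacks one of the two values.

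What counts as Week 12 or Week 16 is set in SAP 2.4: "Assessments are assigned to an analysis window based upon the study day it occurred on as well as the treatment status". In Table 2, Week 12 is "Day 71 to Day 90" and on treatment, which its footnote defines as "After the start of treatment to 1 day after the last dose". Week 16 is any day after Day 90, off treatment, defined as "More than 1 day after the last dose". Table 2 has no early termination (ET) window and no window counted from the last dose. SAP 2.6 adds: "Summary statistics will generally be reported based upon observed data".

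The protocol plans the relevant samples for early stoppers. Section 7.2 calls for an ET visit when study drug is stopped, and says: "Subjects who terminate from the study prior to Study Visit Week 12 will be requested to return to the clinic 28 days" after the last dose, to "complete the equivalent of the Week 16 follow up visit assessments". Sections 8.8 and 8.9 include the serum chemistry panel with GGT at both visits. Section 6.1.3 treats one group differently: subjects who stop drug for persistent gastrointestinal (GI) intolerance stay on the Schedule of Activities.

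SAP 2.7 states that all safety summaries use the ITT population, which SAP 2.1 defines as everyone who received at least one dose.

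**The concern.** A withdrawal flare is a change that follows stopping the drug, so its natural clock starts at the last dose. The SAP uses study-day windows instead. The two agree for a subject who completes 12 weeks. For a subject who stops in the first ten weeks they do not: there is no on-treatment value in the Week 12 window, and the 28-day off-drug draw may come too early for the Week 16 window.

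Subjects are thus selected by how long they stayed on drug, and the reasons for stopping include related Grade 3 or higher adverse events, liver injury criteria (protocol 7.2) and return of ALP to baseline after dose reduction (protocol 7.3, 9.3.8.2). A summary described as covering all treated subjects would in effect cover those still on drug at about Day 70. With at most 30 subjects, a few omissions can change what a descriptive table shows.

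**Working it through.** The plan gives no figure for the flare summary. Its one computed design figure, power of at least 90%, belongs to the primary test. It reproduces (standardized effect 15/25 = 0.6, n = 30, one-sided 5% t-test: 94.1%) and is not touched by this point.

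**Inputs.** Let L be the study day of the last dose and d the day of a draw. SAP Table 2 gives the windows and treatment-status rules. Protocol 7.2 gives an ET draw at stopping (taken here as d = L or L + 1) and a return at d = L + 28. The ±5 days is the Week 16 visit window in protocol Table 1; that it also applies to the early stoppers' return visit is an assumption.

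**Week 12 value.** This needs 71 ≤ d ≤ 90 and d ≤ L + 1. So L + 1 ≥ 71, giving L ≥ 70 if the draw is the day after the last dose, or L ≥ 71 if it is on the same day.

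**Week 16 value.** This needs d > 90, off treatment.
- At 28 days: L + 28 > 90, so L ≥ 63. A last dose on or before Day 62 gives a draw with no window.
- At 23 days: L + 23 > 90, so L ≥ 68, and the cut-off moves to Day 67.
- At 33 days: L + 33 > 90, so L ≥ 58, and the cut-off moves to Day 57.

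**Examples** (ET draw on the day of the last dose):

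| Last dose | ET draw | 28-day draw | Pair? |
|---|---|---|---|
| Day 40 | Day 40, Week 6 | Day 68, no window | No |
| Day 62 | Day 62, Week 8 | Day 90, no window | No |
| Day 65 | Day 65, Week 8 | Day 93, Week 16 | No |
| Day 75 | Day 75, Week 12 | Day 103, Week 16 | Yes |

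Of the 83 possible early-stop days (1 to 83), 69 or 70 give no pair (69/83 = 83.1%; 70/83 = 84.3%). This counts days; it is not a probability, because stops need not be spread evenly.

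**GI stoppers who stay on the Schedule.** With a last dose on Day 40, the Day 84 draw is off treatment (84 > 41) and fits no window. The Day 112 draw is a Week 16 value. There is again no pair, and that value is 112 − 40 = 72 days after the last dose.

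**Late ET draw.** With a last dose on Day 80 and a draw on Day 82, the draw is off treatment (82 > 81) and before Day 91, so it fits no window and there is no pair.

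**Number affected.** No dropout rate is given for this trial. For assumed proportions stopping before about Day 70:
- 5%: 30 × 0.05 = 1.5 subjects
- 12%: 30 × 0.12 = 3.6 subjects
- 30%: 30 × 0.30 = 9 subjects

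Protocol 4.3 reports GI discontinuation of 12% at 1000 mg BID in the 18-week NASH study and none in the PSC study.

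**The case against.** The flare summary is not among the protocol's listed endpoints. It is descriptive, uncontrolled and untested. Restricting it to subjects with about 12 weeks of exposure is a coherent choice, and a separate early-stopper table may hold very few subjects.

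The omitted groups are also hard to interpret. Treatment failures already have ALP back at baseline or higher and may resume pre-study PBC therapy, so their 28-day value may not reflect withdrawal alone. Subjects stopped under the liver criteria start from abnormal values that are followed until they settle. Pooling their falls with completers' values could hide a rise.

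Nor are the values necessarily lost. SAP 3.4.3 refers to a clinical laboratory listing and lists ALT for subjects who meet the liver monitoring threshold. Clinically significant laboratory changes are recorded as adverse events, and adverse events are listed. Liver-injury monitoring results have their own case report form.

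Most of this stands, and it sets the limits of the point. It argues for separate display and a modest priority. It does not argue for leaving the rule as written, because the SAP nowhere says that the summary is meant for completers only, and SAP 2.7 says the opposite.

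A reader might also infer more than the documents support:
- **That every early stopper is excluded.** A stop from about Day 70 with an ET draw within one day of the last dose gives both values.
- **That the excluded subjects are the most likely to flare.** The documents do not say so.
- **That about 4 of 30 will be lost.** The 12% comes from another disease and a longer treatment period, and the same sentence reports no such discontinuations in PSC. This protocol also encourages dose reduction before stopping for GI events.

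**Conclusion.** The point holds in a limited form. As worded, the flare summary in effect leaves out subjects with no on-treatment value in Days 71–90, in practice those whose last dose is before about Day 70. For a last dose on or before Day 62 (Day 57 to 67 across the ±5 days), the 28-day draw also misses the by-window laboratory tables in SAP 3.4.3. GI stoppers who stay on the Schedule have a Week 16 value but no pair.

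Three assumptions matter. That both values are needed is inferred from a difference reported on observed data; it is not stated. The 28-day return is only requested, so the value exists only for those who come back. The number affected cannot be derived from the documents: about 1.5 to 9 of 30 under assumed rates of 5% to 30%.

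This is a cheap improvement to a safety summary. It has no bearing on the primary test or its power.

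**What to change.** In SAP 2.3.8.3 and 3.4.1.1:
- Define the flare change as the last on-treatment value (Week 12 or ET) to the off-treatment value nearest 28 days (±5) after the last dose, for all treated subjects with both values.
- Keep the Week 12 to Week 16 summary for completers. Show early stoppers separately, not pooled, as a table or as a listing if they are few, with days since last dose.
- Say what happens when no off-treatment value falls in the 23 to 33 day range. In the Day 40 example, scheduled visits on Days 56, 84 and 112 are 16, 44 and 72 days after the last dose; such values can be listed with that interval.
- Flag any sample taken after PBC therapy was restarted.

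Separately, protocol 7.3 and 9.3.8.2 let treatment failures resume pre-study PBC treatment, while 6.4.2.1 prohibits UDCA through 28 days after completion. These sections must be reconciled, because they determine what the 28-day value means in those subjects.

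The analysis change costs SAP wording and one small table or listing. It uses the draws already planned and adds no visits. The drawback is that the extra display may hold too few subjects to support more than case-by-case reading.

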## 4. STUDY DESIGN

### 4.1. Overall Design

This is a Phase 2, multicenter, single arm, 12-week open-label proof-of-concept study of HTD1801 in adult subjects with PBC with an inadequate response to standard therapy. Inadequate response is defined as  $ALP \geq 1.5 \times ULN$  despite having been on adequate doses of UDCA for at least 6 months. Up to 30 subjects may be enrolled at up to 20 participating clinical sites.

Subjects may be pre-screened 28 to 56 days prior to the screening day visit using the central laboratory to confirm that their alkaline phosphatase is  $\geq 1.5 \times ULN$  and then will enter a screening period of up to 28 days prior to initiating therapy. Upon confirmation of eligibility, subjects will be enrolled and will receive HTD1801 1000 mg BID for 12 weeks. Study visits will occur at Day 0, Weeks 2, 4, 6, 8, and 12. A final follow-up visit will occur at Week 16, 4 weeks after the last dose of study drug. The Week 2, 4, and 8 visits may be performed remotely (home visits).

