### **8.2. Screening (Days -28 to -1)**

Screening procedures must be completed within 28 days prior to the Baseline visit and can be performed across multiple days during this period. Screening clinical laboratory tests may be repeated once during Screening if the Investigator believes the results to be erroneous. In the event that Screening tests are repeated, the most current results will be used to determine eligibility. If screening procedures are completed and subject eligibility is confirmed, the full 28-day screening period may not be necessary.

During Screening, the following procedures must be conducted and assessments obtained. The information will be collected in the investigational site's standard source documents or in source document templates provided by the Sponsor.

- Informed consent if not obtained at pre-screening visit
- Confirm eligibility criteria
- Demographic information
- Medical history
- Assign subject ID # if not obtained at pre-screening visit
- Complete physical examination
- Vital signs
- Weight, height
- Electrocardiogram, 12 lead (ECG)

- Serum chemistry panel including GGT, Lipid panel — fasting, unsweetened clear coffee, tea or water permitted but no food after supper the evening before
- Complete blood count (CBC) with differential (no smear)
- INR
- Fibrinogen
- CRP
- Haptoglobin
- ELF
- G6PD
- IgM
- IgG
- AMA
- ANA
- TSH
- FSH (if needed to confirm menopausal status)
- Pruritus VAS
- Prior and concomitant medications

Subjects will be instructed to stop all prohibited medications (see Section 6.4) prior to beginning Baseline procedures. In particular, subjects will be cautioned against the use of UDCA until their participation in this study is complete.

NOTE: If the screening ALP value is more than  $\geq 30\%$  lower than the historical value obtained as part of standard of care, the subject will not qualify for enrollment but may be re-screened as soon as 4 weeks later. If on re-screening the ALP value continues to be  $> 30\%$  lower, the subject will not be included in the study.

### 8.3. Baseline/Day 0

Potential subjects who have successfully completed all of the Screening procedures and have met all the eligibility criteria (see Sections 5.1 and 5.2) will be eligible for enrollment in the study. Subjects will undergo the following Baseline procedures and assessments prior to the first dose of study drug:

- Confirmation of continued eligibility
- Update of medical history information

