#### **9.2.4. Vital Signs, Height, and Weight**

Vital sign measurements must be performed at investigational sites by medically qualified individuals according to local requirements. Measurements include blood pressure, pulse, respiratory rate, and body temperature. Blood pressure and pulse will be taken in a recumbent, semi recumbent, or sitting position after 5 minutes of rest. Height (at Screening only) and weight will also be performed. Abnormal findings seen after the start of treatment that the Investigator considers clinically significant are to be reported as AEs.

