#### **9.2.5. Electrocardiograms**

Twelve-lead ECGs will be performed at the investigational site with the subject in a recumbent or semi-recumbent position after 5 minutes of rest. Local institutional standards for QT interval corrections should be utilized. Interpretation of ECG results for the ongoing assessment of safety will be performed by the Investigator or qualified designee during the scheduled visit. Abnormal ECG readings seen after the start of treatment are to be reported as AEs only if they are considered clinically significant by the Investigator. Additionally, the Investigator should consult the Medical Monitor, when possible, for any abnormal, clinically significant ECG findings that may result in a change to the subject's treatment or management.

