#### **12.4.4. Safety Analyses**

Safety endpoints will be summarized using descriptive statistics.

Treatment emergent adverse events (TEAE), events that start on or after the start of treatment, will be summarized by system organ class and preferred term. Summaries of all TEAEs, treatment emergent SAEs, related TEAEs and TEAEs by severity will be produced.

Laboratory, vital sign, and ECG results will be summarized as continuous measures (e.g., change from baseline). Selected laboratory results will also be summarized as categorical variables (e.g., 'in' versus 'out' of the normal range).

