2.3.8.3 Other Safety Endpoints

- Vital signs, height, and weight:
 - Blood pressure, pulse, respiratory rate, height, weight, body temperature, and the presence of clinically significant abnormal values determined by an Investigator. Clinically significant abnormalities identified after the start of treatment will be reported as AEs.
- 12-Lead electrocardiogram (ECG):
 - An Investigator assessment of normal vs abnormal will be available as well as clinically significant vs not clinically significant. Abnormal, clinically significant ECG readings seen after the start of treatment will be recorded as AEs.
- Laboratory samples will include:
 - Hematology, serum chemistry, lipids, coagulation, and other. Clinically significant changes in laboratory values will be recorded by the clinical sites as AEs.
- Post-Treatment Withdrawal Flares:
 - The difference between Week 12 and Week 16 laboratory values for ALP, ALT, AST, and GGT will be summarized.

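### The ECG safety table summarises QT without naming a rate-corrected interval or a common correction formula, so its mean change can reflect heart rate or mixed formulas

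*SAP*

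**What the plan says.** SAP section 3.4.5 sets out the whole ECG analysis. The overall normal or abnormal assessment is tabulated by analysis window, and then: "The QT values will be summarized by analysis window as both the QT value and change from baseline".

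SAP section 2.3.8.3, which describes the ECG data, mentions only the investigator's classification: "An Investigator assessment of normal vs abnormal will be available as well as clinically significant vs not clinically significant". It defines no QT variable, corrected interval, RR interval or ECG heart rate.

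On correction, Protocol section 9.2.5 says: "Local institutional standards for QT interval corrections should be utilized". The reading is also local: "Interpretation of ECG results for the ongoing assessment of safety will be performed by the Investigator or qualified designee during the scheduled visit". Protocol section 12.4.4 treats ECG results as continuous measures but names neither the interval nor a correction.

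On scale, Protocol section 4.1 states: "Up to 30 subjects may be enrolled at up to 20 participating clinical sites". Protocol Table 1 schedules ECGs only at Screening, Week 12 and early termination.

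Pulse is collected as a vital sign under Protocol section 9.2.4: "Measurements include blood pressure, pulse, respiratory rate, and body temperature". SAP section 3.4.4 summarises vital signs and their change from baseline in a separate table.

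**The concern.** QT shortens as heart rate rises and lengthens as it falls. A mean change in raw QT therefore combines any effect on repolarisation with any shift in rate. A rate increase can hide a prolongation, and a decrease can imitate one. If sites enter their own corrected values instead, the column may combine numbers that different formulas would give for identical tracings.

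Safety and tolerability is a stated secondary objective, and this is the only numerical ECG output. For most subjects it will rest on one pre-treatment and one on-treatment tracing, and no control arm is available to subtract a rate shift common to all subjects.

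**Working it through.** The plan gives no QT, QTc or heart-rate figure, so there is nothing of its own to reproduce. The check illustrates the size of each effect.

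**Inputs**

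- From the documents: QT as value and change (SAP 3.4.5); local correction (Protocol 9.2.5); up to 30 subjects at up to 20 sites (Protocol 4.1).
- Assumed: a true QTcF of 410 ms, a starting rate of 70 bpm, and rates between 70 and 90 bpm. Neither document states that HTD1801 changes heart rate.

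**Formulas**, with RR = 60/HR in seconds

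- Fridericia: QTcF = QT / RR^(1/3), so at constant QTcF, QT = 410 × (60/HR)^(1/3)
- Bazett: QTcB = QT / RR^(1/2)

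**Reading 1: the table holds raw QT.** True QTcF is held at 410 ms.

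| Heart rate (bpm) | Raw QT (ms) | Change from 70 bpm (ms) |
|---|---|---|
| 70 | 389.5 | – |
| 72 | 385.8 | −3.6 |
| 73 | 384.1 | −5.4 |
| 80 | 372.5 | −17.0 |

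A fall from 70 to 60 bpm gives 410.0 − 389.5 = +20.5 ms, an apparent prolongation with no change in repolarisation.

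Conversely, suppose raw QT stays at 389.5 ms while rate rises from 70 to 80 bpm. Then QTcF at 80 bpm is 389.5 / 0.75^(1/3) = 428.7 ms. It has risen by 18.7 ms and the table shows zero.

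**Reading 2: the table holds site-corrected values.** The same tracings, with QTcF at 410 ms:

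| Heart rate (bpm) | Raw QT (ms) | QTcB (ms) | QTcB − QTcF (ms) |
|---|---|---|---|
| 70 | 389.5 | 420.7 | 10.7 |
| 80 | 372.5 | 430.1 | 20.1 |
| 90 | 358.2 | 438.7 | 28.7 |

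These are differences in absolute value. If a site uses Bazett throughout and rate goes from 70 to 80 bpm, its within-subject change is off by 20.1 − 10.7, or about 9.5 ms before rounding. For a 3 bpm rise it is about 3 ms. With no rate change the difference cancels completely.

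**Can the pulse table stand in for a correction?** Pulse may be taken recumbent, semi-recumbent or sitting (Protocol 9.2.4), while the ECG is recumbent or semi-recumbent (9.2.5). Under the SAP 2.4.1 rule, baseline pulse would normally come from Day 0, when vital signs are repeated. Baseline QT would come from Screening, the only scheduled pre-treatment ECG. The pulse table can show a mean rate shift, but it does not give the rate on the tracing being analysed.

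**The case against.** The SAP never says the values are uncorrected, and the protocol expects sites to apply a correction. A reader might infer that the plan both leaves QT uncorrected and pools different site formulas. The documents do not support both for one table. If raw QT is tabulated, site formulas affect only the local normal or abnormal reading. If site-corrected values are tabulated, the raw-QT masking does not apply. This stands, and the two effects must not be added.

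The illustration can also be made to look too large. Random rate variation within subjects largely averages out of a mean, so only a systematic shift biases it, and a shift of 2 or 3 bpm is worth about 4 to 5 ms. The Bazett–Fridericia gap shrinks in change scores. This stands too, and is why a range is given.

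A reader might further infer that a QT signal would go unseen. That goes too far. A systematic rate shift should appear in the pulse summary. Each ECG is read by the investigator, clinically significant abnormalities are reported as adverse events, and the Medical Monitor is to be consulted, when possible, on those that may change treatment or management. Recognition of an individual case does not depend on this mean. None of this, however, corrects QT for each subject or tells the reader of the table which quantity it contains.

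**Conclusion.** The point holds as a gap in the specification of a descriptive safety output. Following the SAP literally gives a rate-dependent raw QT summary. The looser reading gives a column that may mix formulas.

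Under the assumed QTcF of 410 ms and start of 70 bpm, a systematic rise of 2 to 10 bpm moves mean raw QT by about −4 to −17 ms with no repolarisation change. Under the other reading, formula differences are about 11 to 20 ms in absolute value at 70 to 80 bpm, and smaller in change from baseline where a site keeps one formula. The sizes depend on those assumptions; the direction does not.

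It would be too strong to call the mean change uninterpretable on either reading, given the partial cancellation and the separate pulse summary. No hypothesis test rests on this table, and the primary ALP analysis is untouched. It is a cheap and worthwhile improvement, not a threat to the study's conclusions.

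**What to change.** In SAP section 3.4.5, state that QTc will be derived in programming by one prespecified formula, for example Fridericia, from the QT and the RR interval or ventricular rate on the same tracing. Summarise the QTc value and its change from baseline by analysis window, and keep raw QT in the listing. Define these variables in SAP section 2.3.8.3. Local correction can remain for the on-site reading under Protocol section 9.2.5.

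Counts of subjects in QTc categories are optional. The documents set no limits, so any used would have to be prespecified.

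The cost is SAP wording and, if ECG rate is not already captured, one eCRF field. The documents do not show the eCRF, so that should be checked first. The change does not remedy the single scheduled on-treatment ECG or the lack of a control arm.
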